### Criterion-based “event” tables

Threshold values of interest for liver function tests are given below.

**Table 7-6 Hepatic events**

Parameter	Criterion
ALT	>3xULN; >5xULN; >8xULN; >10xULN
AST	>3xULN; >5xULN; >8xULN; >10xULN
ALT or AST	>3xULN; >5xULN; >8xULN; >10xULN
TBL	>1.5xULN; >2xULN
DBL	>1.5xULN; >2xULN
TBL and DBL	TBL>1.5xULN+(DBL>ULN, >1.5xULN or >2xULN) TBL>2x ULN+(DBL>ULN, >1.5xULN or >2xULN)
ALP	>2xULN; >3xULN
(ALT or AST) & (TBL or DBL)	ALT or AST >3xULN & TBL or DBL >2xULN ALT or AST >5xULN & TBL or DBL >2xULN ALT or AST >10xULN & TBL or DBL >2xULN

Parameter	Criterion
ALP & (TBL or DBL) (ALT or AST) & (TBL or DBL) & ALP	ALP >3xULN & TBL or DBL >2xULN AT >3xULN & TBL or DBL > 2xULN & ALP < 2xULN (potential Hy's Law case) Note: elevated ALP may suggest obstruction as a consequence of gall bladder or bile duct disease; ALP may also be increased in malignancy. FDA therefore terms Hy's Law cases as indicators of pure hepatocellular injury. This does not mean that cases of AT >3xULN & TBL >2xULN & ALP ≥ 2xULN may not result in severe drug-induced liver injury (DILI).

AST = Aspartate aminotransferase; also known as SGOT, ALT = Alanine aminotransferase; also known as SGPT, ALP = Alkaline phosphatase, TBL = Total bilirubin, DBL = conjugated (direct) bilirubin

The laboratory results meeting specified criteria standard table will be used to provide the number and percentage of patients having AST, ALT > 3, 5, 8, 10 x ULN or TBL >1.5, 2 x ULN or ALP > 2, 3 x ULN.

The number and percentage of potential Hy's Law cases will be presented by treatment group. Potential Hy's Law cases are defined as those patients with AST, ALT >3xULN & TBL >2xULN & ALP <2xULN at the same lab measurement.

### Shift-tables

A cross-tabulation of baseline and worst post-baseline values by below, within and above normal range categories will be provided. Shift tables will be provided for the parameters AST, ALT, TBL, direct bilirubin and ALP. These summaries will be presented by laboratory test and treatment group.

### Standard laboratory change from baseline tables

The lab standard tables will be produced on all the laboratory parameters including changes from baseline in liver parameters. Continuous liver function test values will be plotted over time and analyses of covariance adjusting for covariates will also be performed.

### Adverse event tables

Selected groupings (e.g., SMQ, HLG, HLT) of adverse events, as defined in the CRS will be presented including the respective preferred term frequencies.

Notable events may be defined as liver-related death (Non-cardiovascular death due to liver failure); liver transplantation (from the SAEs and AEs); liver-related study drug discontinuation (from the AEs); any of the 3 events.

The relative risk of the selected groupings (e.g., SMQ, HLT, HLG) on each of the active treatment dosages relative to control will be calculated with 95% confidence intervals.

The number and percentage of patients with selected groupings of adverse events will be presented.

## Graphical displays

For all patients with liver values (AST, ALT, ALP, TBL) matching the thresholds of 5xULN and Hy's Law (Table 7-6), single patient LFT profile graphs will be generated showing all AST, ALT, ALP, TBL lab values reported for this study and the time of study treatment for these patients. An evaluation of Drug Induced Serious Hepatotoxicity (eDISH) plot will also be created.

### 7.4.3 Malignancy

Occurrence of malignancies as adjudicated by the blinded adjudication committee will be summarized based on whether they are

- Primary type (by MedDRA high level group term/high level term including secondary paths and preferred terms)
- Newly detected or represent an existing malignancy
- Whether the patient's history includes this malignancy
- Evidence of metastases and their stage
- Whether the presentation was considered typical or atypical
- Whether and which risk factors there were
- Whether the malignancy was considered unusual and was the response to therapy as expected.

Malignancies from adverse event reports will be identified using the list of search criteria in the CRS. They will be reported as part of the safety analyses described in section 7.3.1. Preferred terms will be reported to allow assessment of the occurrence of malignancies by site.

The analyses discussed below will be performed separately based on the CEC confirmed malignancies, the investigator reported AEs of malignancies, and the investigator reported SAEs of malignancies, if feasible. Time-to-event analyses will be conducted and Kaplan-Meier type plots will be presented. This will also be done for non-cardiovascular deaths due to malignancy.

To assess whether there is an imbalance when follow-up becomes longer, time-to-first event will be explored looking at  $\leq 2$  years of follow-up versus  $>2$  years of follow-up, separately. This will be explored in a Cox regression model including treatment, follow-up ( $\leq 2$  years or  $> 2$  years) and the interaction term as covariates.

Following analyses will also be presented by time period (from randomization to  $\leq 3$  months post-randomization,  $> 3$  to  $\leq 6$  months,  $> 6$  to  $\leq 9$  months,  $> 9$  to  $\leq 12$  months,  $> 12$  to  $\leq 18$  months,  $> 18$  to  $\leq 24$  months,  $> 24$  to  $\leq 30$  months and so on in 6 month intervals for as long as at least 15% of the trial population are still at risk.

- The number of patients at risk, the number of patients with the specified event, and %
- Annualized event rate (AER) with associated 95% CI. The annualized event rate (AER) is calculated as the total number of patients with specific event divided by the cumulative exposure of time to the first specified events.

#### 7.4.4 Thrombocytopenia

Effects with respect to thrombocytopenia will be assessed by the laboratory analyses described in [section 7.3.2](#), additionally criteria for decreased platelet counts per CTC grades as shown in [table 7-7](#) will be reported and baseline platelet counts will be taken into account in this analysis. Shifts versus baseline will also be shown per CTC grade.

**Table 7-7 NIH CTC version 4.0 grades for platelets**

CTC terms	Grade 1	Grade 2	Grade 3	Grade 4
Platelet count decreased	<LLN-75,000/mm  ; <LLN-75.0 x 10  /L	<75,000- 50,000/mm  ; <75.0 - 50.0 x 10  /L	<50,000 - 25,000/ mm  ; <50.0 - 25.0 x 10  /L	<25,000/mm  ; <25.0 x 10  /L

The occurrence of the groupings of adverse events will be analyzed using Cox regression as described in [section 7.2](#) also adding the baseline platelet count to the model and looking for an interaction with treatment.

The baseline use of antithrombotic medications will be evaluated as a subgroup and treatment by subgroup interactions will be evaluated for both the occurrence thrombocytopenia (AE of special interest) and bleeding events (Haemorrhages SMQ), using Cox regression.

Time to the 1st-occurrence of CTC grades ≥3, and time to the 1st-occurrence of bleeding events will be plotted over time using Kaplan-Meier type graphs. A negative binomial regression, as described in [section 7.2](#), will be used to analyze the occurrence of the bleeding events over time. A repeated measures analysis will be performed on the continuous platelet counts change from baseline with the following factors/covariates: treatment, time, time by treatment interaction, time since index MI, randomization plan, and baseline platelet count. Platelet counts change from baseline will also be plotted over time.

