- constitutes a congenital anomaly/birth defect
- requires inpatient hospitalization or prolongation of existing hospitalization, unless hospitalization is for:
 - routine treatment or monitoring of the studied indication, not associated with any deterioration in condition
 - elective or pre-planned treatment for a pre-existing condition that is unrelated to the indication under study and has not worsened since signing the informed consent
 - treatment on an emergency outpatient basis for an event not fulfilling any of the definitions of an SAE given above and not resulting in hospital admission
 - social reasons and respite care in the absence of any deterioration in the patient's general condition
- is medically significant, i.e. defined as an event that jeopardizes the patient or may require medical or surgical intervention to prevent one of the outcomes listed above
 - In CACZ885M2301, malignancies are considered medically significant. This classification will aid in the data collection on these events.

Study-specific adaption of the standard definition of AEs and SAEs

[REDACTED]
[REDACTED] any cardiovascular
[REDACTED]

event sent for adjudication as a potential study endpoint or reported as a non-adjudicated cardiovascular endpoint by the investigator will not be reported as an adverse event /serious adverse event but will be captured on the Clinical Endpoint Form eCRF. Only if the adjudication committee determines that the event is not a study endpoint, will this event be reported as an adverse / serious adverse event following procedures described in [Section 7.2](#) Serious adverse event reporting.

The study specific exemption does not apply to the extension phase. During the extension phase ALL adverse events will be reported as AEs following the procedures described in [Section 7.1](#) and [Section 7.2](#). No adjudication of events will take place during the extension phase.

Unlike routine safety assessments, SAEs are monitored continuously and have special reporting requirements; see [Section 7.2](#).

All adverse events should be treated appropriately. Action taken may include one or more of the following: no action taken (i.e. further observation only); study drug dosage temporarily interrupted; study drug permanently discontinued; concomitant medication given; non-drug therapy given. The action taken to treat the adverse event should be recorded on the Adverse Event CRF.

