If the SAE is not previously documented in the Investigator's Brochure or Package Insert (new occurrence) and is thought to be related to the Novartis study drug, a Drug Safety and Epidemiology Department associate may urgently require further information from the investigator for Health Authority reporting. Novartis may need to issue an Investigator Notification (IN) to inform all investigators involved in any study with the same drug that this SAE has been reported. Suspected Unexpected Serious Adverse Reactions (SUSARs) will be collected and reported to the competent authorities and relevant ethics committees in accordance with EU Guidance 2011/C 172/01 or as per national regulatory requirements in participating countries.

Reporting of events (including coincidental cardiovascular events) that are both study endpoints and AE's / SAE during pivotal phase

The integrity of the pivotal phase may be compromised if cardiovascular events that are study endpoints are systematically unblinded in order to fulfill European SUSAR reporting requirements for SAE ([European Commission ENTR/CT12 Guideline \(2006\)](#)). Therefore, in the pivotal phase, potential study endpoints are excluded from the definition of AE's and SAE's and are not to be captured as AE and SAE's but only on the relevant study endpoint CRF. During the pivotal phase, these events are therefore NOT to be reported to Novartis within 24 hours on SAE forms and will not be reported to regulatory agencies or investigators other than as a study endpoint in the Clinical Study Report. Reporting to IRB's should follow local guidelines.

The following pre-defined study endpoints are excluded from the definition of AEs and SAE's in the pivotal phase:

- CV and non-CV Deaths (please see section Reporting of Deaths for specific exceptions for selected non-CV deaths that must be reported as both endpoints AND SAEs)
- Fatal and non-fatal MI
- Fatal and non-fatal Stroke (e.g. hemorrhagic stroke, ischemic stroke)
- [REDACTED]
- [REDACTED]
- Hospitalization or prolongation of hospitalization for heart failure
- Critical Limb ischemia

- Limb amputation
- Transient Ischemia Attack (TIA)
- New onset type 2 diabetes (NOD)
- [REDACTED]
- Coronary angiography / Coronary Revascularization (PCI or CABG)
- [REDACTED]
- [REDACTED]

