Hemorrhagic: A stroke due to a hemorrhage in the brain as documented by neuroimaging or autopsy. This category will include strokes due to primary intracerebral hemorrhage (intraparenchymal or intraventricular), ischemic strokes with hemorrhagic transformation (i.e.; no evidence or hemorrhage on an initial imaging study but appearance on a subsequent scan), subdural hematoma*, and primary subarachnoid hemorrhage.

[figure not shown]
[figure not shown]
*All subdural hematomas that develop during the clinical trial : should be recorded and classified as either traumatic versus non traumatic.

[figure not shown]
Unknown: the stroke type could not be determined by imaging or other means (e.g. Lumbar puncture, neurosurgery, or autopsy) or no imaging was performed

Stroke Disability

Stroke disability can be classified using an adaptation of the modified Rankin Scale as follows:

- 0: No symptoms at all
- 1: No significant disability despite symptoms; able to carry out all usual duties and activities
- 2: Slight disability; unable to carry out all previous activities, but able to look after own affairs without assistance
- 3: Moderate disability; requiring some help, but able to walk without assistance
- 4: Moderately severe disability; unable to walk without assistance and unable to attend to own bodily needs without assistance
- 5: Severe disability; bedridden, incontinent and requiring constant nursing care and attention
- 6: Dead

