PROC GENMOD DATA=events;
  CLASS treatment(ref='Placebo') <trial part & time since index MI>;
  MODEL <number of events> = treatment
    <trial part & time since index MI> / OFFSET=<log time at risk>
```

```
DIST=NB LINK=LOG LRCI;  
RUN;
```

As matching summary statistics, events per 100 patient years of follow-up will be reported. For selected events, additional potentially predictive covariates will be added to the model, namely at least age, sex, race and region. When selecting repeated events it has to be ensured that a single adverse event case report form entry is only counted once (e.g. by ensuring only one record per adverse event sequence number is counted), as analysis dataset may contain multiple records for one CRF report to allow identification via e.g. different SMQs.

When such a model is used for specific adverse events of interest and a sufficient number of events to make this display useful is available, these data will also be displayed graphically as events per unit time of follow-up for different time intervals (e.g. first 6 months, 6 months – 1 year, 1 year to 2 years ... or smaller time intervals as appropriate) using meaningful categories of time to show time patterns of event occurrence and potential changes in treatment effect over time. Measures of uncertainty will be provided, as well as information on the extent of overdispersion / population heterogeneity.

Changes from baseline in continuous safety parameters will be plotted over time based on both trial parts using repeated measures mixed model. The following SAS code illustrates the statistical model and methods intended for this analysis:

```
proc mixed data=dataset;  
  class patient visit treatment <trial part>  
    <time since index MI>;  
  model <change from baseline> = treatment visit treatment*visit  
    baseline <trial part>  
    <time since index MI>  
    / s ddfm=kr;  
  repeated visit / subject = patient type = un;  
run;
```

with appropriately transformed values. Comparisons of each dose to placebo at each visit will be conducted if feasible. Additional analyses will add potentially predictive covariates, namely age, sex, race, region, education, exercise level, alcohol use, smoking history, BMI and hypertension to the model. The following variables will be analyzed on the log-scales and results will be back-transformed to report geometric means and ratios of geometric means versus placebo:

- [REDACTED]

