#### **Adverse events (AEs) excluding trial endpoints**

The incidence of treatment emergent AEs (events started on the first dose of study medication or events present prior to start of double-blind treatment but increased in severity based on preferred term, up-to/including the earlier date of 119 days after the last study injection or the EOS visit of the core phase) excluding trial endpoints will be summarized by primary system organ class (SOC), preferred term and also by severity and relationship to study treatment. Standardized MedDRA Queries (SMQs) may also be employed. The MedDRA version used for reporting the study will be clearly identified.

Any adverse events reported by the investigator with the onset date after randomization and up-to/including the end of core phase visit and prior to clinical database lock will be included in AE analyses irrespective of how long after last study drug intake. Adverse events occurring after a patient's end of core phase visit will be reported as part of the washout phase/long-term safety extension phase.

If a patient reported more than one AE with the same preferred term, the AE with the greatest severity will be presented. If a patient reported more than one AE within the same primary system organ class, the patient will be counted only once with the greatest severity at the system organ class level, where applicable.

The number and percentage of patients reporting any AE during the double-blind phase of the study will be summarized by primary system organ class, preferred term and treatment. The most common adverse events reported (reported by  $\geq 2\%$  of patients in any group for each preferred term or  $\geq 2\%$  in any group for each SMQ) table will be presented in descending frequency starting from the most common event.

[figure not shown]
Separate summaries will be provided for AEs suspected by the investigator to be related to study drug, deaths, SAEs, and AEs leading to discontinuation.

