#### 7.4.1 Infections / opportunistic infections

Infections as adjudicated will be summarized based on the adjudicated information including whether the infection was classified as opportunistic, whether the infection was typical or atypical based on the patient's medical history, response to standard antibiotic therapy, whether it was a chronic recurrent infection/exacerbation of a previous infection and the presence of risk factors for infections.

The analyses below will be conducted separately for each of the followings if feasible

- Adjudication committee confirmed infections
- All investigator reported AEs of infection (independent of adjudication)
- All investigator reported SAEs of infection (independent of adjudication)

Additionally, all investigator reported infections will be identified using a list of search criteria in the CRS which will be stored in CREDI. The occurrence of such events will be reported by MedDRA preferred term.

These will be classified by severity, seriousness, whether intravenous antibiotics were required (report of use of i.v. antibiotic as a concomitant medication), whether infection AEs/SAEs were suspected to be related to study drug by the investigator and whether study drug was discontinued due to infections. Non-cardiovascular death due to infection/sepsis will also be analyzed. Time to first infection will also be analyzed both in a stratified Cox regression model, as well as using Kaplan-Meier type analyses.

Since infections are expected to be sufficiently frequent in a long-term study to allow the use of multiple covariates, age, sex, race, and region will be added to the Cox regression models stratified by time to index MI and trial part.

The following analyses will also be presented by time period (from randomization to  $\leq 3$  months post-randomization,  $> 3$  to  $\leq 6$  months,  $> 6$  to  $\leq 9$  months,  $> 9$  to  $\leq 12$  months,  $> 12$  to  $\leq 18$  months,  $> 18$  to  $\leq 24$  months,  $> 24$  to  $\leq 30$  months and so on in 6 month intervals for as long as at least 15% of the trial population are still at risk:

- The number of patients at risk, the number of patients with the specified event, and %
- Annualized event rate (AER) with associated 95% CI. The annualized event rate (AER) is calculated as the total number of patients with specific event divided by the cumulative exposure of time to the first specified events.

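### The bleeding analyses in SAP 7.4.4 draw on adverse event records, so adjudication-confirmed hemorrhagic strokes fall outside them

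*SAP*

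**What the plan says.** SAP 7.4.4 (Thrombocytopenia) plans three analyses of bleeding:

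- Cox models testing whether baseline antithrombotic use modifies the treatment effect on "both the occurrence thrombocytopenia (AE of special interest) and bleeding events (Haemorrhages SMQ), using Cox regression".
- A Kaplan-Meier type graph of time to first bleeding event.
- A negative binomial regression, by reference to SAP 7.2, that "will be used to analyze the occurrence of the bleeding events over time".

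No source other than the SMQ is named.

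On the reporting side, Protocol 7.2 lists endpoints that do not count as adverse events or SAEs in the pivotal phase, and the list includes "Fatal and non-fatal Stroke (e.g. hemorrhagic stroke, ischemic stroke". Protocol 7.1 gives the route back: "Only if the adjudication committee determines that the event is not a study endpoint, will this event be reported as an adverse" or serious adverse event. Protocol 15.4 defines the hemorrhagic category: "This category will include strokes due to primary intracerebral hemorrhage (intraparenchymal or intraventricular), ischemic strokes with hemorrhagic transformation", together with subdural hematoma and primary subarachnoid hemorrhage.

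SAP 7.3.1 follows the same division. Treatment-emergent adverse events "excluding trial endpoints will be summarized by primary system organ class (SOC), preferred term", and events from the investigators' endpoint pages get a separate summary by treatment group. That summary has rows for primary hemorrhagic intracerebral stroke, infarction with hemorrhagic conversion, and death due to intracranial hemorrhage.

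**The concern.** Thrombocytopenia is a listed safety topic in SAP Table 7-4, and anti-platelet therapy is part of the background care. SAP 7.4.4 therefore asks a sensible question: does canakinumab change bleeding, and does it do so differently in patients on antithrombotics? Confirmed hemorrhagic stroke is among the most serious answers to that question, yet the event set appears to leave it out.

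The selection also runs the wrong way. A suspected stroke that the committee rejects returns to adverse event reporting and, if coded as a hemorrhage, counts as a bleed. A confirmed hemorrhagic stroke does not. A patient with a confirmed non-fatal one stays in the risk set with no bleeding event, and a patient who dies of one as the first bleed leaves it without an event. A bleeding hazard ratio near 1 would say nothing about this class of bleed, though a reader of 7.4.4 alone could take it as covering all bleeding.

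**Working it through.** The plan states no figure that depends on this point, so there is none to reproduce. The check is a trace of where each kind of record goes.

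**Step 1: what the SMQ searches.** SAP 7.4.4 does not say outright that only adverse event pages are searched. Three places point that way:

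- SAP 7.2, to which the negative binomial model refers, discusses SMQ identification in terms of adverse event forms: "it has to be ensured that a single adverse event case report form entry is only counted once".
- Protocol 8.3 names medical history and adverse events as the data coded in MedDRA.
- The paragraph in 7.4.4 just before the antithrombotic one is about groupings of adverse events.

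**Step 2: where each type of intracranial bleed is recorded in the pivotal phase.**

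| Event | Record | In the 7.4.4 bleeding set? |
|---|---|---|
| Hemorrhagic stroke, confirmed by adjudication | Endpoint page only (Protocol 7.1, 7.2) | No |
| Confirmed, but atypical and suspected by the investigator to be drug-related | Endpoint page and SAE (Protocol 7.2) | Yes |
| Suspected stroke, rejected by adjudication | Returned to AE/SAE (Protocol 7.1) | Yes, if coded as a hemorrhage |
| Traumatic intracranial bleed | Outside the stroke definition (Protocol 15.4), so AE/SAE | Yes |

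**Step 3: fatal events.** Protocol 7.2 lists causes of death that are reported as both endpoint and SAE. The list covers non-cardiovascular deaths, and intracranial hemorrhage is not on it. Other deaths adjudicated as non-cardiovascular are reported as SAEs afterwards, but Protocol 15.1 classes stroke death, intracranial hemorrhage included, as cardiovascular. Neither rule recovers a fatal hemorrhagic stroke.

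**Step 4: other analyses.** SAP Table 6-1 and 6.3.1 analyze fatal or non-fatal stroke as a component of MACE, with ischemic and hemorrhagic strokes together. The endpoint-page table in SAP 7.3.1 separates the subtypes but is a summary by arm. No visible inferential analysis isolates hemorrhagic stroke; parts of the SAP are redacted.

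**Step 5: illustration of size (assumed inputs).** Let s be the share of placebo-arm bleeds that are confirmed hemorrhagic strokes. Then

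combined rate ratio = (1 − s) × RR(other bleeds) + s × RR(hemorrhagic stroke).

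With RR(other bleeds) = 1.0:

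| s (assumed) | RR(hemorrhagic stroke) = 2.0 | RR(hemorrhagic stroke) = 3.0 |
|---|---|---|
| 2% | 0.98 + 0.04 = 1.02 | 0.98 + 0.06 = 1.04 |
| 5% | 0.95 + 0.10 = 1.05 | 0.95 + 0.15 = 1.10 |
| 10% | 0.90 + 0.20 = 1.10 | 0.90 + 0.30 = 1.20 |
| 20% | 0.80 + 0.40 = 1.20 | 0.80 + 0.60 = 1.40 |

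The adverse-event-only ratio is 1.00 in every cell. The table also shows that at a small share a merged ratio barely moves, so merging alone does not solve the problem.

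**The case against.** Five points can be made against this.

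1. **The adverse-event-only source is inferred.** SAP 7.3.1 applies the narrow Ischaemic heart disease SMQ to deaths from endpoint pages, so endpoint records can be searched by SMQ, and data set specifications were still to be written. This stands in part: the reading is a strong inference and not stated text. But 7.3.1 says explicitly when it searches endpoint deaths, and 7.4.4 does not.
2. **The events are in the safety report.** This stands. A reader might infer that hemorrhagic strokes disappear from safety reporting. They do not: SAP 7.3.1 tabulates them, and under Protocol 7.2 the DMC sees endpoint data unblinded. They are absent only from the bleeding hazard ratio, curve, rate and interaction.
3. **Not every intracranial bleed is missing.** This also stands. A reader might infer that the analysis contains none. As Step 2 shows, traumatic, rejected and dual-reported bleeds still enter.
4. **Bleeding is a supporting look.** It has no entry of its own in SAP Table 7-4, and no decision rule in the SAP rests on it. This limits the consequence but does not make the event set right.
5. **Other sections do not merge endpoint events either.** In SAP 7.4.1, "Non-cardiovascular death due to infection/sepsis will also be analyzed"; SAP 7.4.3 treats malignancy deaths in the same way. These are additional analyses, not additions to the adverse event set. That is correct, and it supports a separate hemorrhagic stroke analysis at least as much as a merged one. Section 7.4.4 has neither.

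**Conclusion.** The point holds for a defined class: hemorrhagic strokes confirmed by adjudication, fatal or not, that were not also reported as SAEs. On the natural reading of SAP 7.4.4 they are left out of the antithrombotic interaction model, the Kaplan-Meier curve and the negative binomial rate. This rests on the SMQ being run on adverse event records only, which the SAP implies but does not state.

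The size cannot be derived. It is tempting to apply guessed shares of stroke and of hemorrhagic stroke to the 1,400 patients with MACE and compare the result with a guessed number of serious bleeds. The documents give none of those inputs, and 7.4.4 does not restrict the SMQ to serious events, so such a percentage would describe something the plan does not analyze. The 1.02 to 1.20 range for a doubled hemorrhagic stroke rate shows the direction and nothing more. The SAP should be changed; the primary efficacy analysis is unaffected.

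**What to change.** In SAP 7.4.4:

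- Define a bleeding event as a Haemorrhages SMQ adverse event, a stroke adjudicated as hemorrhagic under Protocol 15.4, or a death due to intracranial hemorrhage. Count each event once, so that dual-reported events are not doubled. Use this set for the Cox, Kaplan-Meier and negative binomial analyses.
- Report time to adjudicated hemorrhagic stroke or intracranial hemorrhage death by arm as a separate component, because a merged estimate can dilute it.
- Within that component, show ischemic strokes with hemorrhagic transformation separately. Protocol 15.4 counts them as hemorrhagic, while SAP 7.3.1 labels them as infarctions with conversion. They begin as ischemic events, which the treatment is hoped to reduce, so they could offset a true excess of bleeding.
- Keep the adverse-event-only set as a sensitivity analysis, and state its source.

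No new data are needed. The cost is a short SAP edit, some extra programming, and de-duplication between endpoint and adverse event records.
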